**Secondary Endpoints**

We will determine whether RARC is superior to ORC in terms of blood loss. More specifically, the overall blood loss due to surgery will be compared between the two treatment arms. In the ORC group the average blood loss is 575 ml . 288 patients yield 90% power to detect a difference of blood loss between the two treatment groups of 20%. These calculations are based on the assumption that the amount of blood loss is normally distributed, that the average blood loss in the open surgery group is 575ml, and that the standard deviation of blood loss is 300ml. A one-sided significance level of 0.025 was used.

We will determine whether RARC is superior to ORC in terms of transfusion rates. The transfusion rates (proportion of patients requiring blood transfusions) will be compared between the two treatment arms. The transfusion rate for ORC is approximately 75%(from Table 2, unpublished). 288 patients yield 92% power and a one-sided significance level of 0.025 to detect a difference of transfusion rates between arms of at least 20%. These calculations are based on the assumption that the transfusion rate is binomially distributed.

*Table 2 (Preliminary Data from University of Texas Health Sciences Center, San Antonio)*

|  | ORC (n=12)  | RARC(n=12)      | p-value |
|--|-------------|-----------------|---------|
| Median (IQR) Units of Blood Given | 2.5 (1-5)   | 0 (0-3)         | 0.082   |
| Transfusion given (%)             | 9/12 (75%)  | 4/12 (33%)      | 0.041   |
| Median (IQR) LOS (days)           | 6.5 (6-8.5) | 6.5 (5-9.5)     | 0.554   |
| LOS (5 days or less)              | 0/12 (0%)   | 4/12 (33.3%)    | 0.028   |
| Median No. LNs (IQR)              | 19 (6-27)   | 10.5 (8.5-17.5) | 0.30    |
| Positive margin                   | 3/12 (25%)  | 0/12 (0%)       | 0.064   |

*All positive margins in the ORC group had pT4 disease.*

Length of hospital stay will be used as a surrogate for recovery after surgery. We will determine whether RARC is superior to ORC in terms of length of hospital stay. Currently, all of the patients receiving ORC stay in the hospital for more than 5 days while 67% of patients in the RARC group stay in the hospital for more than 5 days (from Table 3, unpublished). 288 patients yield 97% power and a one-sided significance level of 0.025 to detect a difference in percent of patients requiring a hospital stay beyond 5 days between RARC and ORC arms of at least 20%. These calculations are based on the assumption that the percent patients requiring a hospital stay beyond 5 days is binomially distributed.

Table 3 (Preliminary Data for Cost Analyses from University of North Carolina)

|                          | ORC (n=21) | RARC (n=20) | P VALUE                |
|--------------------------|------------|-------------|------------------------|
| Age (median)             | 70         | 70          |                        |
| OR time (mins)           | 293        | 389         | <0.001                 |
| OR fees (dollars)        | 5441       | 6202        | <0.00001               |
| OR disposables (dollars) | 2485       | 3715        | = 0.0003               |
| OR capital + reusables   | 50         | 2000        |                        |
| LOS (days)               | 6          | 4           | =0.02(mann whitney U)  |
| Room and Board           | 5954       | 3664        | =0.005 (mann whitneyU) |
| Overall Costs            | 19047      | 19837       | =0.14(mann whitney U)  |

Hand Grip Strength at 3 months after surgery will be measured as a surrogate for recovery after surgery. It was found that only 39% of patients recovered at three months after a major abdominal surgery as measured by the Hand Grip Strength. We will compare the proportion of patients recovered as measured by Hand Grip Strength between the two treatment arms. We hypothesize that 20% more patients will have recovered three months after surgery in the RARC arm compared to the ORC arm. A total of 288 patients yield 91% power and a one-sided significance level of 0.025 to detect a difference between arms of at least 20%. These calculations are based on the assumption that Hand Grip Strength at three months is binomially distributed. Surgical margin as a measure for local cancer control will be measured as positive or negative for each patient and compared between arms using a Fisher's exact test. The number of nodes resected in each arm will be compared using a t-test.

Progression-free and overall survival will be evaluated using the method of Kaplan Meyer and comparisons between arms will be made using the stratified log-rank test.

All efficacy and QL endpoints will be assessed using the PP population.

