### Submission and processing of specimens

The cystectomy specimen (with or without uterus, ovaries, or vaginal cuff in females and prostate in males) will be submitted en bloc, processed and assessed in a standardized fashion at all the participating institutions for margin status along with histology, size, stage, grade and presence/absence of lymphovascular invasion. At a minimum the LND will be submitted in two separate packets labeled left and right pelvic. All of these regions may be submitted in smaller packets (e.g. external iliac, obturator, internal iliac) at the surgeons preference. The standardized Cystectomy Pathology Form will be submitted to CRAB.

The perioperative care measures will be performed per institutional standard based on each institution's policy.

**Progression free survival:** From the date of surgery to the date of first documentation of progression or death due to any cause. Patients last known to be alive and progression-free are censored at the date of last contact. Progression will be determined using RECIST 1.1 criteria by the treating physician based on radiographic or pathologic evidence of disease progression, or death from disease. Any documented recurrence will be considered progression. All patients will have been followed for at least 2 years and 65% of patients will have been followed for 3 years.

**Overall survival:** From date of surgery to date of death due to any cause. Patients last known to be alive are censored at the date of last contact.

Serum hemoglobin and a comprehensive metabolic panel (CMP) will be measured on 10 cc of blood obtained by a venipuncture. These laboratory parameters are part of a routine preoperative work up and postoperative follow up in patients undergoing radical cystectomy and urinary diversion. No extra laboratory tests will be administered to the subjects enrolled in this trial.

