**Clinical Procedures**  
Measurements of Study Endpoints

Measurements of the study end points will be conducted according to the following Table 1:

Table 1: Study Calendar

| Assessment  | Baseline
(Preoperative)          | Hospital
Discharge
(±2 weeks) | 4-6
Weeks    | 3
months     | 6
months     | 12
months | 24
Months | 36
Months |
|---|-------------------------------------|-------------------------------------|-----------------|-----------------|-----------------|--------------|--------------|--------------|
| Baseline History and Physical Exam, Consent, Screening, ECOG Performance Status, TURBT findings | √                                   |                                     |                 |                 |                 |              |              |              |
| Randomization   | √ (within 60 days prior to surgery) |                                     |                 |                 |                 |              |              |              |
| Progression Free Survival   |                                     |                                     |                 |                 |                 | √            | √            | √            |
| Overall Survival  |                                     |                                     | √               | √               | √               | √            | √            | √            |
| Activities of Daily Living (ADL) score  | √                                   |                                     | √
(±30 days) | √
(±30 days) | √
(±30 days) |              |              |              |
| Instrumental Activities of Daily Living (IADL) score  | √                                   |                                     | √
(±30 days) | √
(±30 days) | √
(±30 days) |              |              |              |
| Hand Grip Strength Test   | √                                   |                                     | √
(±30 days) | √
(±30 days) | √
(±30 days) |              |              |              |
| Timed Up and Go Walking Test  | √                                   |                                     | √
(±30 days) | √
(±30 days) | √
(±30 days) |              |              |              |
| Hemoglobin, BMP, serum albumin  | √                                   |                                     | √               | √               | √               | √            | √            | √            |

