### Power and Significance

The margin for this study is 15% which means that RARC would be considered inferior if the true progression free survival at two years was more than 15% lower than the progression-free survival at two years in the ORC arm. A total of 288 evaluable patients (144 patients per arm) yield a study with 80% power and a two-sided significance level, alpha, of 5% to correctly reject the null-hypothesis of unacceptable inferiority. These calculations are based on the assumption that progression-free survival at two years in the patients receiving ORC is approximately 71% and that the rate of progressions at two years is binomially distributed. Evaluable patients are defined as eligible patients who have no major protocol deviations and have 90-day post-surgery follow-up data. Major protocol deviations will be recorded for patients with no surgery given, where surgery was started correctly but discontinued before cystectomy was completed; or where the patient received a surgery type different from their randomization assignment for any reason. In addition, a major protocol deviation will be recorded if the surgery begins as assigned, but the robotic procedure is aborted and an open procedure is required to complete the operation.

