### **Accrual and Study Duration**

We anticipate participation of 15 sites and an accrual of approximately 110 eligible patients per year. Assuming a maximum drop-out rate of 10%, a total of approximately 350 patients (approximately 175 patients in each arm) will be accrued to this study. Thus approximately 350 patients will be accrued in approximately three years. All patients will be followed for at least two years for progression. Based on the accrual estimates, after three years of accrual and two additional years of follow-up, 65% of patients will have follow up available to evaluate progression free survival at 3 years. Thus the study duration is expected to be approximately five years.

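### The powered transfusion comparison has no named test and no covariate, so it gives up a little precision that baseline haemoglobin, already collected, could supply

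*Combined protocol and SAP*

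**What the plan says.** **Endpoint.** Section 5, Secondary Endpoints, sets out to show that RARC is superior to ORC on transfusion. The whole description of the analysis is: "The transfusion rates (proportion of patients requiring blood transfusions) will be compared between the two treatment arms".

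**Power.** The control rate is given as "The transfusion rate for ORC is approximately 75%(from Table 2, unpublished"), which is 9 of 12 pilot patients. The claim is "288 patients yield 92% power and a one-sided significance level of 0.025 to detect a difference of transfusion rates between arms of at least 20" percent, and "These calculations are based on the assumption that the transfusion rate is binomially distributed". The 288 come from Power and Significance: "A total of 288 evaluable patients (144 patients per arm").

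**Haemoglobin.** The Study Calendar (Table 1) has a row "Hemoglobin, BMP, serum albumin" with a baseline tick, and Data Submission Procedures lists the matching form among those due within a week of enrolment. On the blood tests, section 4 says: "These laboratory parameters are part of a routine preoperative work up". In section 5 haemoglobin appears only as an outcome series analysed with mixed models. It is not among the balancing factors, which are diversion type (Treatment/Intervention Plan) and clinical T stage and neoadjuvant chemotherapy (Stratification Factors).

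**Analysis set.** All efficacy endpoints use the per-protocol population. That population requires receipt of the assigned surgery, and Power and Significance counts a robotic-to-open conversion as a major deviation. ITT is planned only as a sensitivity analysis of the primary endpoint.

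**The concern.** For a given blood loss, a patient who starts with lower haemoglobin can be expected to be transfused more readily. Perioperative care follows each institution's policy and no common transfusion trigger is stated, so starting haemoglobin is a natural prognostic covariate for this endpoint. A formal superiority claim that leaves it out has a larger standard error than the collected data allow.

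Two further matters are at stake. Because the method is unnamed, the choice between an adjusted and an unadjusted result is still open when the data arrive. By contrast, the same section names Fisher's exact test for margins and a t-test for node counts. In addition, the per-protocol set is formed after randomization, so it does not carry the full protection of the random allocation, and no ITT version of the transfusion result is planned as a check.

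**Working it through.** **Inputs from the documents.** n = 144 per arm; p1 = 0.75 (ORC); p2 = 0.55 (20 points lower); one-sided alpha 0.025, so z = 1.96.

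**Assumption.** The odds ratio (OR) for transfusion per standard deviation (SD) lower haemoglobin is not in the documents. The main range is 1.5 to 2.5; 1 (no association) and 4 are used as outer limits.

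**1. The stated 92%.**
- Null SE = sqrt(2 × 0.65 × 0.35 / 144) = 0.0562
- Alternative SE = sqrt((0.75 × 0.25 + 0.55 × 0.45) / 144) = sqrt(0.435 / 144) = 0.0550
- Uncorrected: (0.20 − 1.96 × 0.0562) / 0.0550 = 1.63, power 94.9%
- Continuity-corrected (subtract 1/144 = 0.0069 from 0.20): 1.51, power 93.4%
- Exact Fisher: 93.6%

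The corrected and exact versions lie within 2 points of 92%, so the plan's figure stands and is slightly cautious.

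**2. Variance reduction from adjustment.** 4,000 trials were simulated per scenario at 144 per arm. Each was analysed with a logistic model on arm and standardised haemoglobin, giving a standardised (marginal) risk difference. The stratification factors were not simulated here. Let r be the variance of the adjusted risk difference divided by that of the unadjusted one, at 75% v 55%.

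| Assumed OR per SD | r | Unadjusted power | Adjusted power |
|---|---|---|---|
| 1.0 | 1.00 | 94.7% | 94.7% |
| 1.5 | 0.97 | 94.4% | 95.1% |
| 2.0 | 0.90 | 94.4% | 96.4% |
| 2.5 | 0.87 | 94.5% | 97.0% |
| 4.0 | 0.79 | 95.2% | 98.4% |

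A separate simulation (3,000 runs per cell, OR 1.5 to 2.5) put the variance reduction at 2% to 15%.

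**3. Analytic check of the gain.** Scaling both standard errors by sqrt(r), power = Φ(a / sqrt(r) − b), where a is the difference over the alternative SE and b is 1.96 × null SE over alternative SE.
- 75% v 55%: a = 3.639, b = 2.005. r = 1 gives 94.9%; r = 0.97, 0.90, 0.87 give 95.5%, 96.6%, 97.1%. Gain 0.6, 1.8, 2.2 points.
- 75% v 60% (a smaller effect, not in the plan; same r): null SE 0.0552, alternative SE 0.0545, a = 2.753, b = 1.986. r = 1 gives 77.9%; r = 0.97, 0.90, 0.87 give 79.1%, 82.0%, 83.3%. Gain 1.2, 4.2, 5.4 points.

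**4. Type I error.** With no surgical effect and a 75% rate, simulated one-sided size over OR 1 to 4 was 2.3% to 3.2% unadjusted and 2.4% to 3.0% for the standardised risk difference. Simulation error is about 0.25 points.

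**5. What an imbalance would do.** With no surgical effect, a difference in mean haemoglobin between arms moves the raw risk difference as follows:

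| Imbalance | OR 1.5 | OR 2 | OR 4 |
|---|---|---|---|
| 0.1 SD | 0.7 points | 1.2 | 2.0 |
| 0.3 SD | 2.2 points | 3.6 | 6.0 |

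For scale, chance imbalance has SD sqrt(2/144) = 0.118, so 95% of trials fall within 1.96 × 0.118 = 0.23 SD.

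**The case against.** The strongest reply is that an unadjusted comparison of two randomized proportions is valid, the endpoint is secondary, and power at the planned effect is already above 90%. The larger gains appear only at 75% v 60%, which is not the plan's design point, and every gain rests on an assumed association. All of this stands, and it limits the size of the point. In partial answer, the 75% control rate comes from 12 patients, so the design point is itself uncertain, and adjustment helps most where power is lower.

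A reader might infer that any haemoglobin imbalance in the per-protocol set would be taken for a surgical effect. The documents do not support that. Chance imbalance is already covered by the 0.025 error rate. Only exclusions related to both arm and haemoglobin would cause bias, and nothing in the plan links conversion or failure to receive the assigned surgery to haemoglobin. Nor would adjustment repair selection on tumour stage beyond what is modelled, operative difficulty or bleeding.

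A reader might also infer that the plan has chosen a raw two-proportion test. It has not: the binomial statement describes the power calculation, and the test is simply unnamed.

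Extending the adjustment to blood loss has no support here. The argument concerns whether a given loss leads to transfusion, not how much blood is lost.

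Two practical objections hold in part. Randomization may precede surgery by up to 60 days, so the baseline value may not describe the patient at operation. A model that also carried about 15 institutions would have about 21 parameters. A check of that model (2,500 runs per cell) kept the power, but size was 2.4% to 3.4% against 1.9% to 2.8% raw, which is a reason to keep the model small.

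**Conclusion.** The point holds as a modest efficiency and robustness improvement. The transfusion comparison is powered but has no specified analysis, and it leaves a collected preoperative covariate unused. Under assumed odds ratios of 1.5 to 2.5 per SD, adjustment lowers the variance of the risk difference by about 2% to 15%. That is worth about 0 to 2 power points at 75% v 55% and 1 to 5 at 75% v 60%, with size near 2.5%. If haemoglobin does not predict transfusion, nothing is gained and essentially nothing is lost.

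Adjustment would also remove the haemoglobin part of any imbalance created by per-protocol exclusions. It would not remove selection on other factors, for which an ITT analysis is the more direct check. The stated power is sound, and no conclusion of the trial is shown to be at risk.

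**What to change.** In section 5, Secondary Endpoints, replace the general statement on comparing transfusion rates with a specified analysis:

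- Fit a logistic regression of transfusion (yes/no) on arm, baseline haemoglobin as a continuous variable, diversion type, clinical T stage and neoadjuvant chemotherapy.
- From that model, estimate the standardised risk difference. Base both the one-sided 0.025 test and the 95% confidence interval on it, so that they cannot disagree, as a test of the conditional odds ratio and an interval for a marginal difference could.
- Report the raw proportions by arm as description.
- Repeat the analysis in the ITT population.
- State in advance how a missing baseline haemoglobin is handled, and record the interval from the baseline sample to surgery.

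The cost is SAP wording, settled before arm-level outcome data are seen. No new data are needed, and the sample size and power statement can stay as they are. The one small downside is that a baseline value taken up to about 60 days before surgery may predict less well, which would shrink the gain but not invalidate the analysis.

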To date, no study has evaluated the outcomes measuring postoperative recovery using objective parameters of functional independence in patients undergoing RARC nor specifically compared it to outcomes following open cystectomy. Studies evaluating short-term Quality-of-Life (QOL) outcome measures following open cystectomy have not been performed yet. Lawrence et al. conducted a prospective cohort study to systematically describe the clinical course and predictors of long-term recovery to preoperative levels of functional independence in patients after major elective abdominal operations, using both self-report and performance-based instrument. They found that a number of clinical factors independently predicted optimal functional recovery. Serious postoperative complications were consistent independent predictors of poorer recovery and longer time to recovery. Poor preoperative physical performance status (ECOG scale), serum creatinine > 1.5 mg/dL and albumin < 3 mg/dL independently predicted poor recovery at 6 months. However, to our knowledge, no one has tested the hypothesis that utilization of the robotic technique would independently improve recovery and result in superior short or long-term QOL outcomes.

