### **Analysis Populations:**

#### **Per Protocol Population (PP Population):**

The per-protocol population includes all patients who have met inclusion/exclusion criteria and received the surgery to which they were randomized. This is the primary efficacy population. All efficacy and QL endpoints will be assessed using this population.

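### The 3-month hand grip comparison could adjust for ECOG status, creatinine and albumin at almost no cost, and should be repeated in the ITT population

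*Combined protocol and SAP*

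**What the plan says.** **Endpoint and test.** Section 5, Secondary Endpoints, takes from a cited study that "only 39% of patients recovered at three months after a major abdominal surgery as measured by the Hand Grip Strength". It continues: "We will compare the proportion of patients recovered as measured by Hand Grip Strength between the two treatment arms". The target is: "We hypothesize that 20% more patients will have recovered three months after surgery in the RARC arm compared to the ORC arm". No test, model or covariate is named, and the state of being recovered is not defined. Section 5 gives no analysis for Timed Up and Go, ADL or IADL, which Section 3 lists under Specific Aim 3.

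**Predictors.** Section 2 reports, from the same cited study, that poor ECOG status, raised creatinine and low albumin "independently predicted poor recovery at 6 months".

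**Collection.** The baseline column of the Study Calendar (Section 4, Table 1) includes "Baseline History and Physical Exam, Consent, Screening, ECOG Performance Status, TURBT findings" and a separate row for the laboratory panel and albumin. Specific Aim 2 lists creatinine and albumin at baseline. None of the three predictors is a balancing factor. Those are diversion type, clinical T stage and neoadjuvant chemotherapy.

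**Population.** Under the PP definition, which turns on the surgery actually received: "All efficacy and QL endpoints will be assessed using this population". The ITT population is assigned to a sensitivity analysis of the primary endpoint only.

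**The concern.** The plan holds baseline information that its own background section treats as prognostic for recovery, and does not say that it will use it. In a fully randomized set, that costs only some precision. Here the comparison is made in a set formed after randomization. Under Power and Significance, patients with no surgery, incomplete surgery, the other surgery type or a robotic procedure completed as open are major deviations and not evaluable. The last of these can occur only in the RARC arm. If patients who leave differ in baseline risk from those who stay, the PP arms are no longer balanced by design.

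The plan's own reasoning makes this relevant. Analysis of Primary Endpoint defends the PP set for a non-inferiority question and describes ITT as the conservative choice for superiority, whereas grip recovery is a superiority hypothesis. Section 2 also warns that the apparent recovery advantage of RARC may come from patient selection.

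**Working it through.** **1. Reproduce the stated power.** Inputs from Section 5: 144 per arm, 39% v 59% recovered (39% taken as the ORC rate), one-sided 0.025, stated power 91%.

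- Null standard error: sqrt(2 × 0.49 × 0.51 / 144) = 0.0589.
- Alternative standard error: sqrt((0.39 × 0.61 + 0.59 × 0.41) / 144) = 0.0577.
- Pooled test: Φ((0.20 − 1.96 × 0.0589) / 0.0577) = Φ(1.464) = 92.8%.
- With continuity correction (subtract 1/144): Φ(1.344) = 91.1%.
- One-sided Fisher exact: 91.3%.

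The stated figure is that of an unadjusted comparison of two proportions, and it is right.

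**2. Precision gained by adjustment.** Simulation, 2,000 trials per scenario, 144 per arm, 39% v 59%. Assumed, not in the documents: three markers with prevalence 20%, 15% and 10%, each with the odds ratio for non-recovery shown.

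| Odds ratio | Variance, unadjusted | Variance, adjusted | Reduction |
|---|---|---|---|
| 2 | 0.00323 | 0.00316 | 2% |
| 3 | 0.00322 | 0.00301 | 6–7% |
| 5 | 0.00319 | 0.00280 | 12% |

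Repeat runs of the same scenarios gave 2% to 15%. As a benchmark, the analytic unadjusted variance is 0.0577² = 0.00333, about 3% to 4% above the simulated values.

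A second calculation uses one binary poor-risk marker (assumed prevalence 20% to 40%, odds ratio for recovery 0.5 to 0.2). Power is 93.8% to 96.1% adjusted, against Φ(0.20 / 0.0577 − 1.96) = 93.4% unadjusted on the same unpooled basis. Adjustment costs no power.

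**3. Effect of imbalance in the PP set.** Bias = (recovery in good-risk patients − recovery in poor-risk patients) × difference in poor-risk prevalence between arms. With assumed prevalence 30%, odds ratio 0.33 and overall recovery held at 39%, recovery is 46.2% v 22.1%, a gap of 24.1 points.

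- 5-point imbalance favouring RARC: 0.241 × 5 = 1.2 points; one-sided error 0.040.
- 10-point imbalance: 0.241 × 10 = 2.4 points; one-sided error 0.061.
- Across all assumed prevalences and odds ratios: 0.8 to 1.7 points (error 0.034 to 0.048) for 5 points, and 1.5 to 3.5 points (error 0.045 to 0.086) for 10.

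**4. Imbalance that conversions could produce.** Remove a fraction c of the RARC arm, of whom a share s is poor-risk. The remaining prevalence is (0.30 − c × s) / (1 − c).

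- c = 3%, s = 50%: 0.285 / 0.97 = 29.4%; bias 0.15 points; one-sided error 0.027.
- c = 10%, s = 100%: 0.20 / 0.90 = 22.2%; bias 1.9 points; one-sided error 0.051.

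**5. Room for exclusions.** About 350 accrued against 288 evaluable leaves 62, and 62 / 350 = 17.7%. The documents do not say how these would divide between arms or by baseline risk.

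**The case against.** The strongest reply is that nothing in the plan is wrong. A comparison of randomized proportions needs no covariates, the power is correctly computed, and the precision gain is modest. That stands.

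A reader might infer that a chance imbalance in frail patients would be mistaken for an effect of surgical approach. It would not, because the significance level already allows for chance imbalance. With 39% recovery in both arms and the same three markers, 20,000 simulated trials gave unadjusted one-sided false-positive rates of 0.023, 0.023 and 0.025 at odds ratios 2, 3 and 5. Only imbalance caused by exclusions can raise the error, and the documents do not link conversion or non-treatment to any of the three markers.

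A reader might also infer that the albumin threshold printed in Section 2 in mg/dL undermines the analysis. It appears only in a background summary, and no eligibility rule, covariate or analysis uses it.

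Two further limits hold. The predictors are reported for 6 months after major abdominal surgery, so their strength for 3-month grip after cystectomy is inferred. The PP definition also does not say outright that conversions leave the set. The evaluability rule under Power and Significance does exclude them, and the two need reconciling.

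Finally, if selection after randomization is the worry, the direct answer is an ITT analysis. That is correct, and the fix includes one.

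**Conclusion.** The point holds as a low-cost improvement to a secondary analysis. The hand grip comparison is planned in the PP population alone and names no covariates, although three recognised predictors will be in the database. The expected gain is about 2% to 15% lower variance, plus partial protection against measured imbalance.

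The bias at issue is probably small: 0.15 to 1.9 points in the conversion scenario, and at most 3.5 points for a 10-point imbalance, against a 20-point target. All these sizes rest on assumed prevalences, odds ratios and exclusion patterns that the documents do not give.

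Adjustment for three baseline measures does not restore randomization, so it complements an ITT analysis and does not replace it.

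**What to change.** In Section 5, Secondary Endpoints, prespecify that the hand grip comparison, and any arm comparison of Timed Up and Go, ADL and IADL, reports a covariate-adjusted difference between arms, for example a standardized risk difference for hand grip recovery. Adjust for baseline ECOG status and for creatinine and albumin as continuous values, and show the unadjusted result beside it. Report the same comparison in the ITT population. Do not adjust for postoperative complications, which arise after surgery.

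The cost is a few sentences and no new baseline data. The text also needs a definition of recovery (required for any analysis of this endpoint), a coding for ECOG and a rule for missing covariates. For the ITT analysis, it needs a rule for patients without a 3-month grip measurement, such as those who had no surgery. The PP definition should also be aligned with the evaluability rule on conversions.

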**B. Performance Related Measures of Functional Independence**

1. Hand Grip Strength Test outcomes at baseline and in the post operative period 4-6 weeks, 3 months, and 6 months.
2. Timed Up and Go Walking Test outcomes at baseline and in the post operative period 4-6 weeks, 3 months, and 6 months.

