## 5. STATISTICAL CONSIDERATIONS

### Study Objective and Primary Endpoint

The primary objective of this study is to compare progression-free survival of RARC versus ORC in patients with bladder cancer. More specifically, the primary endpoint for this study is progression-free survival at 2 years. This is a non-inferiority comparison, i.e. the study will test whether the robotic-assisted cystectomy is, at worst, inferior to the open radical cystectomy by a small pre-defined margin. This study will use a centralized dynamic allocation procedure to allocate an equal number of patients to each of the treatment arms. The procedure will balance the marginal distribution of the stratification factors between these two treatments.

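### Hand grip strength is compared only as a yes/no recovery at 3 months with no stated threshold, which loses about 36-38% of the information under a normal model; a baseline-adjusted mixed model would use the values already collected

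*Combined protocol and SAP*

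**What the plan says.** Section 3 (Specific Aim 3, part B) lists "Hand Grip Strength Test outcomes at baseline and in the post operative period 4-6 weeks, 3 months, and 6 months". Table 1 schedules the test at the same four times, with a ±30-day window on each follow-up visit, and the Data Submission Procedures provide baseline and follow-up forms for it.

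Section 5 treats grip as a secondary endpoint and reduces it to a proportion at one visit: "We will compare the proportion of patients recovered as measured by Hand Grip Strength between the two treatment arms". The control rate comes from a cited cohort, in which "only 39% of patients recovered at three months after a major abdominal surgery as measured by the Hand Grip Strength". The effect is stated as: "We hypothesize that 20% more patients will have recovered three months after surgery in the RARC arm compared to the ORC arm". The power line reads "A total of 288 patients yield 91% power and a one-sided significance level of 0.025", followed by "These calculations are based on the assumption that Hand Grip Strength at three months is binomially distributed".

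The text does not say what grip value, change or tolerance counts as recovered, how a missing 3-month value is handled, or which test compares the proportions. For other repeated measures the plan does give a longitudinal method: under Analysis of Primary Endpoint, linear mixed models are specified for the laboratory values and for FACT-VCI and SF-8.

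**The concern.** Grip strength is a measured quantity with a baseline and up to three follow-up values per patient. The stated analysis keeps one yes/no from one visit. Three things follow.

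- The result depends on a threshold that the text does not fix. Two analysts could classify the same patient differently, for example one a little below the preoperative value.
- Patients far from the threshold and patients just past it count the same, so precision is lost.
- The 4-6 week and 6-month values have no stated analysis.

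At stake is the precision of one secondary comparison, and its chance of detecting a benefit smaller than the 20 points hypothesised.

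**Working it through.** **Inputs from the documents.**
- ORC proportion recovered p1 = 0.39, and a 20-point difference, so p2 = 0.59 (Secondary Endpoints). The 20% is read as absolute. A relative reading gives 0.39 × 1.2 = 0.468 and only 27% power, which does not match the plan.
- n = 144 per arm (Power and Significance), consistent with the aim to "allocate an equal number of patients to each of the treatment arms".
- One-sided level 0.025, so z = 1.960.

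**Assumptions, not in the documents.** Change in grip is normal with the same SD in both arms, and the surgical effect is a pure shift. The baseline to follow-up correlation r is shown from 0.5 to 0.9.

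**1. Reproduce the stated 91%.** The mean proportion is 0.49.
- SE under the null: √(2 × 0.49 × 0.51/144) = 0.0589.
- SE under the alternative: √((0.39 × 0.61 + 0.59 × 0.41)/144) = 0.0577.
- Without continuity correction: Φ[(0.20 − 1.960 × 0.0589)/0.0577] = Φ(1.464) = 92.8%.
- With continuity correction (subtract 1/144 from the difference): Φ(1.344) = 91.1%.
- A one-sided Fisher exact test gives 91.3%.

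The plan's figure is reproduced. For 91% power the binary test needs 144 per arm with the correction, or 134 without it.

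**2. The same effect on the continuous scale.** d = z(0.59) − z(0.39) = 0.2275 + 0.2793 = 0.507 SD of change. Power with 144 per arm: Φ(0.507 × √72 − 1.960) = Φ(2.341) = 99.0%. The like-for-like comparison is with the uncorrected 92.8%, a gain of about 6 points.

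**3. Information lost.** For 91% power the continuous test needs 2 × (1.960 + 1.341)²/0.507² ≈ 85 per arm. Against the uncorrected 134, 1 − 85/134 = 37%. Directly, the efficiency of a cut at proportion p is φ(z_p)²/[p(1 − p)]: 0.619 at p = 0.39, 0.636 at 0.49 and 0.625 at 0.59. The loss is therefore about 36-38%.

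**4. Smaller effects, 144 per arm, no continuity correction.**

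| d | Proportions recovered | Binary power | Continuous power |
|---|---|---|---|
| 0.507 | 39% v 59% | 92.8% | 99.0% |
| 0.40 | 39% v 54.8% | 77% | 92% |
| 0.30 | 39% v 50.8% | 52% | 72% |

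**5. What baseline adjustment adds.** If recovery is judged against the patient's own baseline, d is already in SD units of change. With equal variance s² at both times, a change score has variance 2s²(1 − r) and the baseline-adjusted residual has s²(1 − r²). The ratio is (1 + r)/2: 0.75 at r = 0.5, 0.85 at r = 0.7 and 0.95 at r = 0.9. The number per arm for 91% power falls from 85 to 64, 73 and 81 respectively.

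**The case against.** The strongest case for leaving the plan alone has three parts.

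- **Power is already adequate at the hypothesised difference.** The 91% is correct, and the 288 evaluable patients come from the progression-free survival calculation. This stands. The gain is in precision and in effects below 20 points.
- **The proportion recovered answers the question asked.** The Background names recovery to preoperative independence as the gap, and a percentage can be set beside the cited 39%. A mean difference in grip is a different estimand and needs its own interpretation. This also stands, and is why the proportion should be kept.
- **Recovery is not wholly without meaning.** The Background describes the cited cohort as studying return to preoperative levels, and the form mock-ups in Appendix B are not reproduced in the text. This stands in part. The claim can only be that the supplied text gives no threshold; a description of a cited study does not say how far below baseline still counts as recovered.

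A reader might also infer four stronger things that the documents do not support.

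- *The power statement is wrong.* It is not (step 1).
- *The cut wastes about 40% of the trial's patients.* The 41% comes from 1 − 85/144, which sets an uncorrected calculation against a continuity-corrected one. And because the sample size is set by the primary endpoint, no patients would be saved.
- *Baseline adjustment halves the variance again.* The factor 1 − r² (0.51 at r = 0.7) applies against an unadjusted 3-month value. Against a change score the factor is 0.85, and claiming a halving counts the baseline twice.
- *The threshold will be chosen after the results are seen.* The text leaves room for that, but nothing in it shows such an intention.

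**Conclusion.** The concern holds as a cheap improvement to a secondary endpoint. The only stated grip analysis rests on a threshold that the supplied text does not give; that part needs no assumption. The efficiency loss of about 36-38% depends on a normal change score, a common SD and a shift effect. The documents give no grip SD, distribution or correlation with which to test those assumptions. At the planned effect the loss is modest in power terms, about 6 points. It becomes material if the true effect is smaller: about 15 points at d = 0.40 and 20 points at d = 0.30. The primary progression-free survival conclusion is not affected.

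**What to change.** In Section 5, Secondary Endpoints:

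1. Make the between-arm test of grip a linear mixed model on the measured values at 4-6 weeks, 3 months and 6 months, adjusted for baseline grip, with arm, visit and arm-by-visit terms. Name the 3-month arm contrast as the test, at the one-sided 0.025 level already chosen. This follows the mixed models planned for the laboratory and QOL data. Given the ±30-day window, the visit-timing term planned for QOL could be carried over.
2. Keep the proportion recovered at 3 months as a supporting result. Before analysis, fix its threshold relative to the patient's own baseline, the handling of missing values and the test.
3. Restate the power line for the continuous comparison, giving the standardised difference and the correlation as assumptions with a range.

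The cost is SAP wording and a recalculated power statement, with no new visits, forms or patients. The downside is that the directly interpretable percentage, comparable with the cited 39%, becomes supportive.
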